## 10.5 – Secondary Endpoint #5

Endpoint Description: Tolerability measured as number of subjects developing moderate ( $> 5.5$  mmol/L) or severe ( $\geq 6$  mmol/L) hyperkalemia, using the pre-COVID-19 population.

Response Variable Definition: Number of subjects with a documented event of interest of hyperkalemia defined as potassium  $> 5.5$  mmol/L between Randomization and the Week 24 assessment.

Additional Covariates in Addition to Randomized Treatment: atrial fibrillation status at time of randomization

Handling of Dropouts and Missing Data: Each patient will be evaluated based on the available follow-up. No adjustment for incomplete follow-up will be made.

Sensitivity Analysis: Re-calculate the endpoint analysis using the original ITT population.

Statistical Tests: A logistic regression model (PROC LOGISTIC in SAS) will be used to estimate and statistically compare whether there is differential rate of subjects developing hyperkalemia between the treatments.

Interpretation of Results: A lower rate of developing moderate or severe hypokalemia defined as potassium  $> 5.5$  mmol/L, indicates better tolerance of LCZ696 arm versus Valsartan.

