13.2 Secondary Endpoints

1. Days alive and out of hospital at 6 months, not listed for transplant (status 1A, 1B or 1-4) or undergoing transplant, implanted with an LVAD, maintained or started on continuous inotropic therapy for ≥ 7 days, or has had two hospital admissions for HF (other than the index admission*). If a patient meets the pre-specified secondary endpoint of 2 hospital admissions for heart failure (other than the index admission), the patient can remain on study drug or be started on open label sacubitril/valsartan, at the treating physician's discretion, while remaining in the trial.

*The days alive and out of hospital will end on the day of the second readmission.

2. Tolerability measured as:
 - a) Number of subjects achieving a target dose of 25%, 50% or 100% of valsartan or LCZ696
 - b) Number of subjects developing hypotension (SBP ≤ 85 mmHg) with symptoms
 - c) Number of subjects developing worsening renal function (eGFR < 20 ml/min/1.73 m²)
 - d) Number of subjects developing moderate (≥ 5.5 mmol/L) or severe (≥ 6 mmol/L) hyperkalemia

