15.9 Anticipated Disease Related Events and Events of Interest

The following are anticipated, disease-related events in patients with HF or anticipated events of interest in patients with heart failure taking valsartan or valsartan/sacubitril:

- **Arrhythmias:** This refers to both atrial and ventricular arrhythmias.
- **Sudden Cardiac Death:** This refers to witnessed cardiac arrests and sudden deaths without an otherwise apparent cause such as trauma or malignancy.
- **Acute coronary syndrome:** This refers to unstable angina, non ST segment elevation myocardial infarction (NSTEMI), and ST segment elevation myocardial (STEMI).
- **Unplanned hospitalization, ER visit or clinic visit for worsening HF:** This refers to treatment for acute heart failure such as receiving intravenous diuretics.
- **Cerebrovascular event:** This refers to cerebrovascular accidents (stroke) of any cause (hemorrhagic, ischemic, or embolic) and transient ischemic attack (TIA).
- **Venous thromboembolism:** This includes both deep venous thrombosis and pulmonary embolus.
- **Lightheadedness, Presyncope, or Syncope:** This includes dizziness, lightheadedness, or fainting from any cause.
- **Worsening renal function:** This refers to acute kidney injury, typically defined as a decrease in eGFR \geq 20% over 48 hours, or progressive loss of renal function over time.
- **LVAD implantation:** This refers to implantation of a temporary or durable LVAD.
- **Cardiac Transplantation**
- **Hyperkalemia \geq 5.5 mEq/L**
- **Acute renal failure with serum creatinine $>$ 2.5 mg/dL**
- **Angioedema**
- **Symptomatic hypotension**

Anticipated events will not be captured as AEs/SAEs during the study, but will be entered on the appropriate electronic case report form (eCRF) module (“Events of Interest” page).

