15.10 Recording and Reporting of Adverse Events

The site Investigator is responsible for monitoring the safety of subjects enrolled into the study at the study sites. For this study, non-serious AEs will not be collected on the safety reporting page of the eCRF, but should be documented in the source documents and followed according to local standard of care. Events significant enough to necessitate modification of study drug dosing will be captured on the appropriate eCRF module (“Study Drug Dosing” page).

All SAEs, except for those anticipated events listed above, occurring from signed informed consent through study visit 11 will be captured on the SAE eCRF. Subjects that have screen failed will be followed for SAEs until two weeks post last study drug dose. Unless exempted as described above, all SAEs, whether or not deemed drug-related or expected, must be reported by the investigator or qualified designee within 24 hours of first becoming aware of the event. For this study, the cause of death will be reported on either the SAE or Events of interest (EVNINT) eCRF, as well as the Death eCRF page. The investigator or qualified designee will enter the required information regarding the SAE into the appropriate module of the eCRF, which will automatically result in distribution of the information to DCRI Safety Surveillance. DCRI Safety Surveillance will share all SAE reports with Novartis Pharmaceuticals. If the eCRF system is temporarily unavailable, the event, including the investigator-determined causality to study drug should be reported via the back-up paper SAE form to DCRI Safety Surveillance. Upon return of the availability of the electronic data capture (EDC) system, the SAE information must be entered into the eCRF.

Any misuse or abuse of the study drug, other medication errors and uses outside of what is foreseen in the protocol (irrespective of whether a clinical event has occurred) must also be reported to DCRI.

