##### Secondary Endpoints (Tolerability)

#2: Tolerability measured as number of subjects achieving a target dose of 25%, 50% or 100% of valsartan or LCZ696.

#3: Tolerability measured as number of subjects developing hypotension (SBP  $\leq 85$  mmHg) with symptoms.

#4: Tolerability measured as number of subjects developing worsening renal function (eGFR  $< 20$  ml/min/1.73m^2).

#5: Tolerability measured as number of subjects developing moderate ( $> 5.5$  mmol/L) or severe ( $\geq 6$  mmol/L) hyperkalemia.

See Section 10 for a detailed description of each secondary endpoint, including rules used for handling incomplete data.

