#### **10.4 – Secondary Endpoint #4**

Endpoint Description: Tolerability measured as number of subjects developing worsening renal function (eGFR <20 ml/min/1.73m^2), using the pre-COVID-19 population.

Response Variable Definition: Number of subjects with a documented event of interest of worsening renal function defined as eGFR <20 ml/min/1.73m^2 between Randomization and the Week 24 assessment.

Additional Covariates in Addition to Randomized Treatment: atrial fibrillation status at time of randomization

Handling of Dropouts and Missing Data: Each patient will be evaluated based on the available follow-up. No adjustment for incomplete follow-up will be made.

Sensitivity Analysis: Re-calculate the endpoint analysis using the original ITT population.

Statistical Tests: A logistic regression model (PROC LOGISTIC in SAS) will be used to estimate and statistically compare whether there is differential rate of subjects developing worsening renal function between the treatments.

Interpretation of Results: A lower rate of developing worsening renal function defined as GFR < 20 ml/min/1.73m^2, indicates better tolerance of LCZ696 arm versus Valsartan.

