### **13. Safety analysis**

#### **13.1 – Safety Endpoint #1**

Safety Endpoint #1: Comparison of serious adverse events at the level of MedDRA preferred term, using the pre-COVID-19 population.

Response Variable Definitions: The number of patients experiencing each unique serious adverse event (SAE) type based on MedDRA preferred term within body system.

Additional Covariates: None

Handling of Dropouts and Missing Data: No adjustments for missing data will be made.

Sensitivity Analysis: Re-calculate the endpoint analysis using the original ITT population.

Statistical Tests: Fisher's mid-p will be calculated for each serious adverse event based upon the unique MedDRA preferred term within a body system.

Interpretation of Results: Lower event rates indicate a better outcome for LCZ696 arm versus Valsartan.

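### The SAP counts hyperkalemia above 5.5 mmol/L where the protocol counts it from 5.5; and SAP 10.4 takes eGFR below 20 only from site-reported events that carry no such trigger

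*SAP*

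**What the plan says.** **Potassium.** Protocol 13.2 lists as a tolerability endpoint "Number of subjects developing moderate (≥ 5.5 mmol/L) or severe (≥ 6 mmol/L) hyperkalemia". The Executive Summary and Protocol 4.2 use the same limits, and the event-of-interest list in Protocol 15.9 includes hyperkalemia from 5.5 mEq/L upward (the same number in mmol/L for potassium). SAP 6 introduces the endpoint as "5: Tolerability measured as number of subjects developing moderate" hyperkalemia, with the moderate level strictly above 5.5. SAP 10.5 repeats the strict inequality in its description, its response variable ("Number of subjects with a documented event of interest of hyperkalemia defined as potassium" above 5.5) and its interpretation. That last line reads "A lower rate of developing moderate or severe hypokalemia defined as potassium" above 5.5, so it names the opposite disorder.

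**Where such events are recorded.** Protocol 15.9: "Anticipated events will not be captured as AEs/SAEs during the study, but will be entered on the appropriate electronic case report form". Protocol 15.10: "non-serious AEs will not be collected on the safety reporting page of the eCRF". The single safety endpoint in SAP 13.1 is "Comparison of serious adverse events at the level of MedDRA preferred term".

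**Renal function.** Protocol 13.2 and SAP 6 agree that the endpoint is eGFR below 20 mL/min/1.73 m². SAP 10.4 obtains it as "Number of subjects with a documented event of interest of worsening renal function defined as eGFR" below 20. Protocol 15.9 has two renal items. One is worsening renal function: acute kidney injury, typically an eGFR drop of 20% or more within 48 hours, or a gradual decline. The other is acute renal failure with creatinine over 2.5 mg/dL.

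**The concern.** Hyperkalemia is one of the named tolerability endpoints in a population whose risks the protocol describes as unknown (Protocol 11.6). Which subjects count depends on which document the programmer follows. Sites were told to record an event from 5.5 upward, so a subject peaking at exactly 5.5 can have an event record that the analysis then discards. It will not resurface elsewhere: anticipated events are kept out of the AE/SAE data, the SAP's only safety table is of SAEs, and the SAP has no separate potassium analysis. Protocol 18.1 does plan comparisons of laboratory values for the DSMB, but the SAP specifies none for potassium.

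The renal endpoint raises a different question. Both documents agree on the threshold, but SAP 10.4 reaches it through site-reported items that are triggered by something else. A scheduled laboratory value below 20 need not produce an event record, so need not be counted.

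**Working it through.** The documents state no rate, power or sample size for these endpoints, so there is no planned figure to reproduce. The check is a comparison of texts plus two illustrations.

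**1. Potassium definitions side by side**

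| Place | Moderate | Severe |
|---|---|---|
| Protocol 3, 4.2, 13.2 | ≥ 5.5 | ≥ 6 |
| Protocol 15.9 (event of interest) | ≥ 5.5 | not separated |
| SAP 6, SAP 10.5 | > 5.5 | ≥ 6 (not in the 10.5 response variable) |

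The same SAP lines print ≥ correctly for the 6 mmol/L level, so a symbol lost in text conversion is an unlikely explanation. The severe level agrees. Only subjects whose highest value is exactly 5.5 are affected. Protocol 9.3 excludes potassium above 5.5, so a subject can enter at 5.5.

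**2. How many subjects could sit on the boundary (illustration)**

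From the documents: 335 subjects in the pre-COVID-19 population (SAP 3) and five post-randomisation visits with local laboratory tests, at weeks 2, 4, 8, 12 and 24 (Protocol, Appendix A).

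Assumed: potassium normal with mean 4.4 to 4.6 and SD 0.45 to 0.5, reported to 0.1, within-subject correlation 0.3 to 0.7, every value captured, baseline no higher than 5.5.

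With reporting to 0.1, ≥ 5.5 means a true value above 5.45, and > 5.5 means above 5.55. Given subject level b and within-subject SD s, P(ever above c) = 1 − Φ((c − b)/s)^k for k visits. This is averaged over b, conditional on an eligible baseline.

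| Mean / SD / correlation | ≥ 5.5 | > 5.5 | Difference of 335, k = 5 | k = 4 |
|---|---|---|---|---|
| 4.4 / 0.45 / 0.7 | 2.87% (9.6) | 1.55% (5.2) | 4.4 | 3.8 |
| 4.5 / 0.5 / 0.5 | 9.47% (31.7) | 6.06% (20.3) | 11.4 | 9.9 |
| 4.6 / 0.5 / 0.3 | 16.65% (55.8) | 11.18% (37.5) | 18.3 | 15.7 |

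Across the assumed range, about 0.3 to 3.4 of the subjects counted at ≥ 5.5 would already have been at 5.5 at baseline.

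Effect on the comparison, middle case, assumed shift of 0.1 mmol/L between arms of 167 and 168, with SE of the log odds ratio = √[1/(n₁p₁(1−p₁)) + 1/(n₀p₀(1−p₀))]:
- ≥ 5.5: 14.1% vs 9.5%, odds ratio 1.57, SE 0.345
- > 5.5: 9.5% vs 6.1%, odds ratio 1.62, SE 0.418

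The estimate barely moves; precision falls.

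**3. Renal: does the event item contain the endpoint?**

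Relative fall = (baseline − follow-up)/baseline. A 20% fall ends exactly at 20 when baseline is 20/0.8 = 25. Baselines from 20 to just under 25 are eligible (Protocol 9.3 excludes only below 20).
- 22 to 19: 3/22 = 13.6%. Endpoint met, 20% criterion not met.
- 24 to 19.5: 4.5/24 = 18.8%. Same.
- 60 to 45: 15/60 = 25%. 20% criterion met, endpoint not met.

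Neither definition contains the other. The remaining route for the first two cases is the gradual-decline wording, which has no number and leaves the decision to the site.

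If events occurred at an assumed 8% vs 5% and a fraction c was captured equally in both arms of 167 and 168:
- c = 1: 167×0.08 + 168×0.05 = 21.8 events, odds ratio 1.65, SE 0.45
- c = 0.75: 16.3 events, odds ratio 1.64, SE 0.52
- c = 0.5: 10.9 events, odds ratio 1.62, SE 0.63

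**The case against.** **The strict cut-off may be deliberate.** It matches the eligibility limit in Protocol 9.3 and avoids counting as a new event someone who entered at 5.5 and stayed there. That is a reasonable motive, but the SAP does not state it, although it does explain its COVID-19 and BNP changes. Reporting subjects already at 5.5 at baseline meets the difficulty without departing from the protocol.

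**The subject counts do not model the SAP endpoint.** This stands. SAP 10.5 counts site-documented events; the illustration counts every laboratory value at every visit. Protocol 16.2 expects up to 20–25% of subjects without Week 24 NT-proBNP, and SAP 3 removes some visit data for 25 of the 335. Four visits give about 4 to 16, and incomplete reporting would lower that further. A reader might take 4 to 18 as subjects actually lost; the documents support no such estimate.

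**The renal endpoint may be captured well enough.** Much of this stands. A reader might infer that SAP 10.4 must miss subjects with eGFR below 20, because scheduled visits are too far apart to show a 48-hour fall. The documents do not support that. The 48-hour figure is qualified as typical, the gradual-decline limb is open, and any value below 20 is a fall from an eligible baseline. Unscheduled visits include creatinine, and inpatients may have further tests. The case report form is not among the documents and might record eGFR. Under-capture is possible, not shown.

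**The consequence is small.** Also fair: the illustrative odds ratios hardly change, and nothing indicates that either rule favours one arm.

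**Conclusion.** The potassium contradiction is established on the text. The SAP's rule is narrower than the protocol endpoint it is meant to implement, and it drops subjects peaking at exactly 5.5 without explanation or another planned SAP analysis designed to show them. How many is unknown; the illustrated range rests entirely on assumed distributions and full capture.

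The renal point holds with moderate confidence and in a limited form: for some eligible subjects, whether a visit eGFR below 20 counts depends on whether the site chooses to report it.

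A reader might infer a bias in favour of one treatment from either point. The documents give no basis for that. If capture is equal in both arms, the loss is in counts and precision. These are secondary tolerability endpoints, so this should be corrected but does not bear on the main conclusion.

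**What to change.** **SAP 6 and 10.5.** Change > 5.5 to the protocol's ≥ 5.5, correct *hypokalemia* to *hyperkalemia*, and report how many counted subjects were already at 5.5 at baseline. If the sponsor intended > 5.5, state the reason and report the ≥ 5.5 count beside it. These are text edits plus one extra count. The cost is that a subject who enters at 5.5 and stays there is counted, which the baseline report makes visible.

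**SAP 10.4.** In addition to documented events, count any post-randomisation eGFR below 20 through Week 24, using the visit values already planned for Tertiary Endpoint #9 (SAP 11.9). Keep the event-only count as supportive. No new data collection is needed. The downside is that isolated or spurious laboratory values may be counted. If this is added after unblinding, label it post hoc.

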18 STUDY ADMINISTRATION

18.1 Data and Safety Monitoring Board

A DSMB has been appointed by the NHLBI for the HFN, and will function as the DSMB for this trial. This committee consists of a group of highly experienced individuals with extensive pertinent expertise in HF and clinical trials. The DSMB will advise the HFN Steering Committee regarding the continuing safety of current subjects and those yet to be recruited, as well as the continuing validity and scientific merit of the trial. Safety data, summarized at the treatment level, will be assessed approximately every 3 months by the DSMB. The safety analyses will be based on the entire ITT population. Safety will be evaluated by comparing the occurrence of AEs and changes in laboratory values of the active treatment arm compared to the active

control arm.

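### The SAP counts hyperkalaemia only above 5.5 mmol/L, whereas the protocol endpoint and its event list start at 5.5; the SAP gives no reason for the change.

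*SAP*

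**What the plan says.** Protocol 13.2, item 2d, sets the endpoint as "Number of subjects developing moderate (≥ 5.5 mmol/L) or severe (≥ 6 mmol/L) hyperkalemia". Protocol 4.2 and the executive summary give the same cut-offs. Protocol 15.9 lists hyperkalaemia of 5.5 mEq/L or above as an anticipated event, to be entered on the Events of Interest page of the case report form.

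The endpoint list in SAP section 6 begins "Tolerability measured as number of subjects developing moderate" and then gives > 5.5 mmol/L for moderate and 6 mmol/L or above for severe. SAP 10.5 repeats this in its endpoint description. It defines the response as "Number of subjects with a documented event of interest of hyperkalemia defined as potassium" > 5.5 mmol/L between randomization and the Week 24 assessment, and tests it with one logistic regression adjusted for atrial fibrillation status. The only sensitivity analysis repeats the model in the original ITT population. The interpretation line reads "A lower rate of developing moderate or severe hypokalemia defined as potassium" > 5.5 mmol/L.

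**The concern.** The two documents define one endpoint with different rules. The difference is a single symbol, but it falls on a value that laboratories can report: if potassium is given to one decimal, 5.5 is the lowest value that meets the protocol rule. The event page is defined from 5.5 upward, so a subject whose only documented event is at exactly 5.5 qualifies for the page and for the protocol endpoint, yet is absent from the SAP count.

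At stake is whether the count reported for a secondary tolerability endpoint is the one the protocol defined. Protocol 11.6 lists hyperkalaemia among the adverse reactions of both valsartan and LCZ696, so readers will look at this count. The word hypokalaemia in the interpretation line is a separate slip that could be carried into a table title or footnote.

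**Working it through.** **Step 1. Set the definitions side by side.** For potassium, a monovalent ion, mEq/L and mmol/L are numerically equal.

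| Place | Moderate, or event threshold | Severe |
|---|---|---|
| Protocol executive summary, 4.2 and 13.2 | ≥ 5.5 mmol/L | ≥ 6 mmol/L |
| Protocol 15.9, Events of Interest | ≥ 5.5 mEq/L | not given |
| SAP 6, endpoint #5 | > 5.5 mmol/L | ≥ 6 mmol/L |
| SAP 10.5, endpoint description | > 5.5 mmol/L | ≥ 6 mmol/L |
| SAP 10.5, response variable | > 5.5 mmol/L | not used separately |
| SAP 10.5, interpretation | > 5.5 mmol/L, called hypokalaemia | not used separately |

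**Step 2. Is it a text-extraction fault or a one-off slip?** Neither is likely. SAP 6 and the endpoint description in SAP 10.5 print the strict sign for 5.5 and the inclusive sign for 6 in the same line. The strict sign appears once in SAP 6 and three times in SAP 10.5.

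**Step 3. Was the change explained?** No. The other tolerability cut-offs carry over unchanged (systolic pressure ≤ 85 mmHg, eGFR < 20). The SAP does explain other departures: the pre-COVID-19 population, the dropped 2.5- and 5-fold imputations, and BNP assayed only for the first 200 patients.

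**Step 4. Consequence.** Every subject above 5.5 is also at 5.5 or above, so the SAP count cannot exceed the protocol count. The two differ by the subjects whose highest documented value is exactly 5.5.

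**Step 5. Scale, by assumption only.** The plan states no figure to reproduce and gives no potassium distribution. Assume a per-subject peak that is normal with mean m and SD s, reported to 0.1 mmol/L, in 335 patients (SAP section 3):

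- P(5.5 or above) = 1 − Φ((5.45 − m)/s)
- P(above 5.5) = 1 − Φ((5.55 − m)/s)
- Share at exactly 5.5 = (first − second) / first

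Middle case, m = 4.8 and s = 0.5: 1 − Φ(1.3) = 0.0968, or 32.4 patients; 1 − Φ(1.5) = 0.0668, or 22.4 patients. The difference is 10.0 patients, or 31.0% of those at 5.5 or above.

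Patients at exactly 5.5, with their share of all patients at 5.5 or above:

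| m | s = 0.4 | s = 0.5 | s = 0.6 |
|---|---|---|---|
| 4.6 | 2.7 (47.8%) | 5.3 (35.6%) | 7.2 (27.6%) |
| 4.8 | 7.3 (41.6%) | 10.0 (31.0%) | 11.3 (24.2%) |
| 5.0 | 15.3 (35.1%) | 16.2 (26.3%) | 15.7 (20.7%) |

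Other assumptions move the range. With single measurements of mean 4.3 to 4.7 and SD 0.4 to 0.6 at five independent visits, the share is 22% to 56%, or about 2 to 31 of 335. All these figures model laboratory peaks, whereas the SAP endpoint counts event-page entries.

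**The case against.** **The strict sign may be deliberate.** Exclusion 6 in Protocol 9.3 bars entry only above 5.5, so a subject can be enrolled at exactly 5.5, and an endpoint about developing hyperkalaemia should arguably not count that subject as new. This is reasonable, but the SAP does not say it. The strict rule also drops subjects who rise to 5.5 from a lower baseline. A note on Visit 2 values answers the concern without changing the endpoint.

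**The practical difference could be nil.** The documents do not show whether the event page records a potassium value. If it does not, the two rules cannot be separated in the data. This stands, and it limits the claim about size. It does not reconcile the two definitions.

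**Two stronger readings are tempting, and the documents do not support them.**

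- *That the SAP drops a required severe tier.* Moderate or severe can be read as one count, and values of 6 or above are nested within it, so a single indicator meets the protocol wording. It is true that the serious adverse event table (SAP 13.1, "Comparison of serious adverse events at the level of MedDRA preferred term") cannot show severe cases, because hyperkalaemia is on the anticipated list: "Anticipated events will not be captured as AEs/SAEs during the study" (Protocol 15.9), and "All SAEs, except for those anticipated events listed above" go on the SAE form (Protocol 15.10). That makes a severe row useful, not required.
- *That the endpoint wrongly ignores potassium measured at visits.* SAP 10.3, 10.4 and 10.5 all use documented events of interest, which is a consistent design choice, and no document says that events are under-entered. Protocol 18.1 does mention "comparing the occurrence of AEs and changes in laboratory values", but in general terms and within the monitoring board section. It is also unclear that visit potassium is in the database. SAP 11.9 lists eGFR at week 2, which might suggest that local results were entered, but SAP 11.10 lists cystatin C at week 2 as well, and the protocol schedule has no cystatin C draw then.

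**Conclusion.** The inconsistency is real and minor. The SAP's rule for secondary endpoint #5 is narrower than the protocol's at exactly 5.5 mmol/L, no reason is given, and one word in the interpretation line is wrong. These are facts of the text and need no assumption.

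The number of subjects affected does need assumptions. Under the assumed peak distributions it is about 3 to 16 of 335. That range shows only that the boundary value could matter to the count; it does not estimate what the event page contains. Nothing suggests that the difference favours either arm. The primary analysis and its conclusion are unaffected.

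**What to change.** In SAP section 6 and throughout SAP 10.5, change > 5.5 to ≥ 5.5 mmol/L. Keep the event-page response variable and the logistic model, and correct hypokalaemia to hyperkalaemia. If Visit 2 potassium is in the database, state how many counted subjects already had 5.5 at that visit. If the strict cut-off was intended, the SAP should say so and give the reason.

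Optional, and not the correction of an error: a descriptive count by arm at 6 mmol/L or above from the event page, without a test, if the page records the value. Such counts are likely to be small.

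The response should not be replaced by the highest laboratory potassium. That would redefine a secondary endpoint after the interim efficacy analysis described in SAP section 14, to address a problem that the documents do not show.

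The cost is a few words in the SAP and, where the values exist, one note and one optional table row. No new assessment is needed.
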